4.1.8. Breath Hydrogen Test

Breath hydrogen tests will determine the amount of hydrogen (H_2) and methane (CH_4) present in expired breath following ingestion of a known volume of carbohydrate. The type of gas in expired breath depends on the type of bacteria present in the lower gut. Collection of a timed response will allow future calculation and determination of the amount of unabsorbed

carbohydrate in a meal through gut response measures. Breath hydrogen tests will be conducted at the same time as the time course experiments (insulin, glucose, CCK) and during the first day of the SmartPill testing. Collections are done at 30, 60, 90, 120, and 180 minutes after finishing the test meal, taken into a 30 cc syringe and sealed for later analysis in a Quintron Gas Analyzer.

4.1.9. Fecal Collection

Stool samples will be collected twice during the study, at the beginning and the end of the diet period. Subjects will be instructed in the use of a plastic device to cover the toilet seat and collect the stool. Two separate ~5 g samples will be taken for fecal microbiome analyses. All samples will be transported to the laboratory, coded by the research assistant, and held at -80° C for future microbiome analysis.

4.2. Statistical Considerations

The main endpoint of interest in this study is weight loss. There are several proposed mechanisms by which legumes are thought to promote weight loss, many of which have not been tested in a controlled setting. Due to new technology, we are now able to examine one of these proposed mechanisms—colon transit time, allowing us to directly observe a legume diet's physiologic effect. Previous studies of legume-heavy diets have shown indications that the particular type of fiber specific to legumes may increase satiety and slow gastric emptying significantly, leading patients to consume fewer calories per day, thereby promoting weight loss without intensive intervention from the study staff. Thus, we do expect to have differences in energy intake between groups. The analyses will follow the intent-to-treat principle. BMI will certainly be considered as a possible confounder. Since this is a pilot trial, doing so will be important to determine the appropriate target population for a full-scale trial and whether randomization in that protocol should be stratified by BMI. Secondary outcomes, including both the satiety hormones and glucose are expected to rise quickly in response to the test meal and then decline over the course of the next few hours as gastric emptying occurs.

In the Legume Inflammation Feeding Experiment full-feeding study, participants averaged -3.9 ± 0.4 kg over the course of four weeks⁸. Ten participants (five individuals per treatment arm) would be sufficient to detect a difference of just 1.25kg (we expect > 1 kg) in weight loss, with 80% power, assuming a standard deviation for each groups' weight loss that is slightly higher (± 0.7 kg) than seen in our prior study⁸. To account for the potential small dropout rate, we will recruit a total of 14 patients (7 per treatment arm). There are multiple secondary outcomes that we are interested in determining the appropriate sample size for when we run a full-scale study. Some of these outcomes are novel, so we are exploring the feasibility of pursuing them in a full scale study.

Within-subject changes in end-points will be compared by paired t-test; comparisons between treatment groups by two-sample t-tests. For the time course experiments, because of the large expected individual variations in fasting levels of metabolic and appetite hormones, we intend to compute the change from baseline at each time point for each individual for all of the variables and subsequently comparing the area under the curve results⁵⁵. All data will be presented as means \pm SEM; the probability level at which differences will be considered significant will be $P < 0.05$. All analyses will be performed using the most recent version of SAS (SAS Institute, Cary, NC).

Timeline

	Mo. 1	Mo. 2	Mo. 3	Mo. 4	Mo. 5	Mo. 6	Mo. 7	Mo. 8	Mo. 9	Mo. 10	Mo. 11	Mo. 12
IRB Approval, set up	X	X										
Recruiting			X	X	X	X	X	X				
Follow-up				X	X	X	X	X	X	X		
Biomarker Analysis									X	X	X	X
Statistical Analysis											X	X
Manuscript Preparation											X	X
Report to Funding Agency												X
Draft of Subsequent R01												X

REFERENCES

1. National Center for Health Statistics (NCHS). National Health and Nutrition Examination Survey Data. 2005-2006. *US Dept. of Health and Human Services, Centers for Disease Control and Prevention*. 2007; Washington, DC.

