1. INTRODUCTION

Obesity is a significant public health concern. Nearly two-third of US adults are overweight or obese (body mass index [BMI] ≥ 25 and ≥ 30 kg/m², respectively).¹ It is well known that excess body weight is associated with increased risk for a number of chronic conditions including diabetes, heart disease, and some cancers including colorectal cancer (CRC).

Effective dietary strategies are essential to address the issues of obesity and related metabolic disorders. Diet composition is one factor that could influence dietary energy intake. For example, diets that are high in fiber require more chewing and a greater volume is consumed at a given energy intake (kcal/g). These factors could lead to earlier termination of eating and increased satiation. In addition, fiber-rich diets may impact physiological mechanisms important for weight control including hormone release and gastric emptying.^{2,3}

Epidemiologic research has linked higher legume consumption with reduced risk for obesity² and in some studies, with reduced risk for CRC and the precursor lesions, adenomatous polyps.⁴ In previous research that targeted men at increased risk for CRC we observed that a high-legume diet provided under conditions of weight maintenance favorably influenced biomarkers of inflammation, lipid levels, and gut hormone concentrations.⁵⁻⁹ In the same study, during a 4-week ancillary diet period where participants consumed the full legume diet entrée but with side dishes ad libitum and were allowed to lose weight, the high-legume diet facilitated weight loss.⁸ Participants consumed less total energy (-770 kcal/d below requirements for weight maintenance), lost weight (-4.0 kg; -4.4%) and serum lipid and gut hormone concentrations and biomarkers of insulin sensitivity (plasma glucose: -5.7%; insulin: -15.8%; serum C-peptide: -17.4%) and inflammation (serum CRP: -20.2) all improved significantly. This sub-study was conducted after an intensive 12 week randomized controlled crossover feeding trial but the sub-study itself was not randomized and controlled. We did not have the resources needed to conduct a feeding response time-course experiment or to explore other novel mechanisms through which legumes may facilitate weight loss (e.g. appetite-regulating hormones, gastric emptying and transit time). In addition, the provision of all of the diet components may have played a role in controlling intake and promoting weight loss.

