1.1.1. Primary Objectives

1. Evaluate the effects of a high-legume diet compared to a control diet with a similar macronutrient profile on weight loss in a randomized controlled feeding study conducted over eight weeks.

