2.2.1. Strategies to Recruit and Enroll Participants

Subjects eligible according to a phone interview will be invited to one of the study sites. On this visit, after receiving informed consent, the participant's height, weight, and blood pressure will be checked. All eligible consented participants will be asked to visit the Emory ACTSI site to assess their resting metabolic rate (RMR) to be used to plan meals that will facilitate a weight loss of 1-2 pounds per week (energy deficit ~500-1000 kcal/day). Once their individualized diet plan is developed participants will all undergo a one-week run-in of diet similar to the control diet. The run-in helps to standardize conditions before the baseline biomarker collection and provides some confidence in the participants' ability to adhere to the study protocol.

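### Section 4.2's 80% power with five per arm is about 70% under the planned t-test (taken as two-sided), and the documents do not support a between-diet difference of 1 kg or more

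*Combined protocol and SAP*

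**What the plan says.** The primary objective (1.1.1) is a between-arm comparison: "Evaluate the effects of a high-legume diet compared to a control diet with a similar macronutrient profile on weight loss", over eight weeks.

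The sizing in 4.2 states "Ten participants (five individuals per treatment arm) would be sufficient to detect a difference of just 1.25kg (we expect > 1 kg) in weight loss". It claims 80% power for this, "assuming a standard deviation for each groups' weight loss that is slightly higher (± 0.7 kg) than seen in our prior study". Seven per arm are recruited to allow for dropout, with no dropout rate given. The analysis paragraph of 4.2 specifies two-sample t-tests between groups at the 0.05 level and does not say whether they are one- or two-sided.

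The only weight-loss result in the sizing paragraph is the earlier study's mean loss of 3.9 kg (± 0.4) in four weeks. The Introduction says of that period that "the sub-study itself was not randomized and controlled". It also reports an energy deficit of 770 kcal/day relative to weight-maintenance needs.

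In the present trial, Section 2.2.1 has resting metabolic rate measured in all eligible consenting men in order to "plan meals that will facilitate a weight loss of 1-2 pounds per week (energy deficit ~500-1000 kcal/day"). Section 3.1.2 gives both groups two pre-portioned entrees a day and guidance towards their diet plans, and leaves side dishes uncontrolled.

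**The concern.** A reader of 4.2 would conclude that ten completers give 80% power for the legume effect and that the expected effect is of about the size the trial can detect. Both parts need qualifying.

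The 80% does not match the test that will be run. With eight degrees of freedom, the normal approximation leaves out a material penalty for estimating the SD.

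The expectation of more than 1 kg is a statement about a difference between two diets, but no comparative figure is cited for it. The cited loss had no concurrent control, and the control men here are themselves on a weight-loss plan. No control-arm loss is assumed anywhere, so the documents do not show how much of a legume-arm loss would remain as a difference.

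What is at stake is interpretation. Section 4.2 says the pilot is meant to inform a full-scale trial, and the timeline ends with a draft of a further grant application. If the primary test is described as having 80% power, a null weight result could be taken as evidence against a legume effect, or the next trial could be sized on an unsupported difference.

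**Working it through.** **Inputs** (all from 4.2 unless noted): difference d = 1.25 kg; SD s = 0.7 kg in each arm; n = 5 per arm, 7 recruited; α = 0.05, taken as two-sided (assumption); two-sample t-test.

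**1. Reproduce the plan's figure (normal approximation).**

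n per arm = 2 × [s × (1.960 + 0.842) / d]² = 2 × [0.7 × 2.802 / 1.25]² = 4.92, rounded up to 5.

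Power at n = 5 is Φ(d/s × √(n/2) − 1.960) = Φ(2.823 − 1.960) = 80.6%. Both the ten participants and the 80% reproduce.

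**2. Use the planned test.** Power is the probability that a noncentral t variable, with 2n − 2 degrees of freedom and noncentrality d/s × √(n/2), falls outside ± the 97.5% point of the central t. At d = 1.25 kg:

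| n per arm | df | critical t | noncentrality | power |
|---|---|---|---|---|
| 5 | 8 | 2.306 | 2.823 | 69.7% |
| 6 | 10 | 2.228 | 3.093 | 79.6% |
| 7 | 12 | 2.179 | 3.341 | 86.5% |

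The difference detectable with 80% power is 1.42 kg at 5 per arm and 1.14 kg at 7. The fall from 80.6% to 69.7% comes wholly from using the t in place of the normal distribution. It has nothing to do with the control arm.

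**3. Vary the difference** (same t-test, SD 0.7 kg):

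| true difference | 5 per arm | 7 per arm |
|---|---|---|
| 0.5 kg | 17% | 23% |
| 0.75 kg | 32% | 45% |
| 1.0 kg | 51% | 69% |
| 1.25 kg | 70% | 87% |

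**4. What the documents imply about the difference.** The range below is illustrative and is not an estimate. Over the four weeks for which a legume figure exists, men meeting a plan of 1 to 2 lb/week would lose 4 × 0.4536 = 1.81 kg to 8 × 0.4536 = 3.63 kg. If a legume group again lost 3.9 kg and controls met their plan, the difference would be 3.9 − 3.63 = 0.27 kg to 3.9 − 1.81 = 2.09 kg. If both arms met the same plan equally, it would be zero. If controls fell short of their plan, it would be larger. The documents do not say which of these is likely.

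**5. What a non-significant result could exclude.** With an observed SD of 0.7 kg, the 95% CI half-width is critical t × s × √(2/n). That is 2.306 × 0.7 × √(2/5) = 1.02 kg at 5 per arm and 2.179 × 0.7 × √(2/7) = 0.82 kg at 7. With five per arm, even an observed difference of zero would not exclude 1 kg.

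**The case against.** The strongest defence is that the power statement is conditional on 1.25 kg and an SD of 0.7 kg, and that on those inputs it reproduces. This stands for the normal approximation. A control arm on a deficit plan leaves the chosen difference unsupported, but it does not make a conditional power figure wrong. A one-sided 5% t-test at 5 per arm would also exceed 80% (82.4%), so the 70% depends on reading the unstated sidedness as two-sided. In addition, if all 14 men complete, t-test power at 1.25 kg is about 87%; the shortfall applies to the ten-participant claim.

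Three stronger readings are tempting, and the documents do not support them.

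- *That 1.25 kg was derived from the 3.9 kg loss.* Section 4.2 never says so. It uses the earlier study explicitly only for the SD, and 1.25 kg is about a third of 3.9 kg, so an undocumented discount cannot be excluded. The Introduction refers the energy deficit, not the weight loss, to maintenance needs.
- *That the plan contradicts itself by expecting more than 1 kg and sizing for 1.25 kg.* An open lower bound of 1 kg is compatible with 1.25 kg.
- *That power is really only about 6%, because the midpoint of the control plan (750 kcal/day) nearly equals the earlier 770 kcal/day.* That calculation credits controls with full adherence while fixing the legume men at 770 kcal/day, although both arms get the same kind of plan and guidance and side dishes are uncontrolled. It shows that the difference is unknown, not that power is low.

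It is also fair to say that this is a pilot and that no go/no-go rule on weight appears. That limits the consequence. It does not remove the need for the stated power to match the planned test.

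**Conclusion.** The point holds in two separate parts. (a) For the planned t-test, taken as two-sided at 5% with SD 0.7 kg, power at 1.25 kg with five per arm is about 70%, roughly ten percentage points below the figure stated. It reaches about 80% at six per arm and 87% at seven. (b) The documents give no support for a between-diet difference of 1 kg or more when both arms follow a guided but unenforced deficit plan. The true difference could be above or below 1.25 kg, so 80% power for the comparison actually made is not assured. This does not establish that the trial is underpowered for the true effect, since that effect is unknown.

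All these powers depend on the 0.7 kg SD. Section 4.2 does not say what the ± 0.4 kg from the earlier study is, and it plans to report means with SEMs. If it were an SEM, the SD would be 0.4 × √n for a sub-study size the documents do not give. An assumed n of 10 to 65 gives an SD of 1.26 to 3.22 kg, and t-test power at 1.25 kg of 28% down to 8% with 5 per arm, or 40% down to 10% with 7. That is a separate question, and the reason the revised figures should be labelled conditional on the SD.

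**What to change.** Change 4.2 only, and leave enrolment at 14.

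- Replace the 80% claim with two-sided t-test power at SD 0.7 kg for differences of 0.5, 0.75, 1.0 and 1.25 kg: 17%, 32%, 51% and 70% with 5 per arm; 23%, 45%, 69% and 87% with 7 per arm. State that the test is two-sided and that the figures are conditional on the SD.
- Remove the bracketed expectation of more than 1 kg, or justify it as a difference between two arms that both follow a deficit plan.
- State that the primary result will be the between-arm difference in weight loss with its 95% CI, and that a non-significant difference will not be read as absence of a legume effect.

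The cost is a rewritten sizing paragraph and one sentence on interpretation, with no extra participants, visits or procedures. The downside is a less favourable stated power.

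### Section 4.2 claims 80% power with five men per arm, but the planned t-test, read as two-sided at 5%, has about 70%; neither the formula nor the sidedness is stated

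*Combined protocol and SAP*

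**What the plan says.** All the relevant text is in Section 4.2, Statistical Considerations.

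- **Power claim.** Ten men, five per arm, "would be sufficient to detect a difference of just 1.25kg (we expect > 1 kg) in weight loss, with 80% power".
- **Variability.** The calculation is made "assuming a standard deviation for each groups' weight loss that is slightly higher (± 0.7 kg) than seen in our prior study".
- **Recruitment.** "To account for the potential small dropout rate, we will recruit a total of 14 patients (7 per treatment arm"). No dropout rate is given.
- **Analysis.** The plan specifies "comparisons between treatment groups by two-sample t-tests", and "the probability level at which differences will be considered significant will be" P < 0.05.

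Weight loss is the primary outcome (Sections 1.1 and 1.1.1), so this t-test is the one the power claim must describe. The documents do not name the formula or software behind the sample size, and they do not say whether the test is one- or two-sided.

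**The concern.** With five men per arm the t-test has only 8 degrees of freedom. Its two-sided 5% critical value is 2.306, against 1.960 for the normal distribution. A sample size taken from a normal formula will therefore overstate the power of the planned test, and at this size the overstatement is not small.

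Two things are at stake. First, the plan treats ten evaluable men as sufficient and the other four as cover for dropout; if ten are not sufficient, part of that cover is already needed to reach 80%. Second, the pilot is meant to inform a full-scale study. A null result in ten men would be read against a stated 20% chance of missing the target difference, when the chance under a two-sided test is about 30%. A reader should also be able to reproduce the calculation, and without formula or sidedness that takes guesswork.

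**Working it through.** **Inputs, all from Section 4.2.** Difference 1.25 kg; SD 0.7 kg in each arm; 5 per arm; claimed power 80%; two-sample t-test; significance level 0.05. Sidedness is not stated, so both readings are computed.

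**Step 1: reproduce the plan's figure.** The two-sided normal approximation gives

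n per arm = 2 × [SD × (1.960 + 0.842) / difference]² = 2 × (0.7 × 2.80 / 1.25)² = 4.92, rounded up to 5.

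The standard error with 5 per arm is 0.7 × √(2/5) = 0.443 kg. Power is Φ(1.25/0.443 − 1.960) = Φ(0.863) = 80.6%, and the difference detectable with 80% power is 0.443 × 2.80 = 1.24 kg. This matches the stated 5 per arm, 80% and 1.25 kg, so it is the likely source.

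**Step 2: power of the planned test, two-sided.** Under the alternative, the t statistic follows a noncentral t distribution with n₁ + n₂ − 2 degrees of freedom and noncentrality 1.25 / [0.7 × √(1/n₁ + 1/n₂)]. With 5 v 5, the noncentrality is 1.25/0.443 = 2.82 on 8 degrees of freedom. Power is the probability of exceeding 2.306, which is **69.7%**. A simulation of 200,000 trials gave 69.9%; the unequal-variance form of the test gave 67.3% in the same simulation.

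In kilograms: at an SD of 0.7 kg, significance needs an observed difference of about 2.306 × 0.443 = 1.02 kg with the t critical value, against 1.960 × 0.443 = 0.87 kg with the normal one.

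**Step 3: the same test at the splits that 14 recruits could leave.**

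| Evaluable men | Losses from 14 | df | Noncentrality | Two-sided power |
|---|---|---|---|---|
| 7 v 7 | 0 | 12 | 3.34 | 86.5% |
| 6 v 7 | 1 | 11 | 3.21 | 83.2% |
| 6 v 6 | 2 | 10 | 3.09 | 79.6% |
| 5 v 7 | 2 | 10 | 3.05 | 78.5% |
| 5 v 6 | 3 | 9 | 2.95 | 74.7% |
| 5 v 5 | 4 | 8 | 2.82 | 69.7% |

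**Step 4: what would give 80% with a two-sided t-test.**

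| Per arm | Detectable difference at SD 0.7 kg | Largest SD for 1.25 kg |
|---|---|---|
| 5 | 1.42 kg | 0.617 kg |
| 6 | 1.26 kg | 0.696 kg |
| 7 | 1.14 kg | 0.766 kg |

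**Step 5: the one-sided reading.** A one-sided 5% t-test with 5 per arm has 82.4% power and a detectable difference of 1.21 kg. With 4 per arm it has 72.0%, so five is also the smallest number reaching 80% on that reading.

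**The case against.** The strongest reply has four parts.

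1. **The 80% is not a slip.** It follows from a standard formula. That is true, and it explains the figure. It does not make the figure right for a t-test on 8 degrees of freedom, where the approximation overstates power by about 11 points (80.6% against 69.7%).

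2. **The test may have been meant as one-sided.** The hypothesis in Section 2 is directional, and a one-sided t-test supports five per arm. This cannot be excluded, so the 70% is conditional. But no section states a one-sided test, the primary objective in Section 1.1.1 is worded neutrally, and an unqualified P < 0.05 is ordinarily read as two-sided. If one-sided was intended, the plan still has to say so.

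3. **The trial recruits 14, not ten.** This stands. The full shortfall needs four of 14 men (29%) to be lost, two from each arm, while the plan expects little dropout. The run-in before randomization (Sections 2.2.1 and 3.1.1) may remove some poor adherers. Weekly weights (Section 3.1.2) and the intent-to-treat principle may keep some leavers in the analysis, although no missing-data rule is given. The objection limits the consequence; it does not rescue the statement that five per arm suffice.

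4. **The SD matters more.** Section 4.2 sets 0.7 kg by reference to a prior result of 3.9 ± 0.4 kg without saying whether ± is an SD or an SEM. As an illustration only, an SD of 1.5 kg would give 21% power at 5 v 5 and 30% at 7 v 7. This is a separate question, but any restated power must be labelled as conditional on the 0.7 kg.

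**Conclusion.** The concern holds. Taken as two-sided at 5%, with the plan's own 1.25 kg difference and 0.7 kg SD, the planned t-test has 69.7% power with five men per arm, about 10 points short of the stated 80%. The recruitment total is not undermined: the 14 men meet 80% with no loss or one loss and nearly meet it with two (79.6% or 78.5%). What is wrong is the number called sufficient and the losses it implies the trial can absorb, which is about one per arm rather than two.

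The arithmetic is firm. The two-sided reading is an assumption, though the usual one, and the normal approximation as the source of the 80% is inferred. That the plan omits both formula and sidedness is a matter of record. The point should be fixed, but it does not call for a change of design.

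**What to change.** In Section 4.2, state the formula or software used for the sample size and whether the primary test is one- or two-sided. If two-sided, replace the power claim with wording such as:

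> With a two-sided 5% two-sample t-test and an assumed SD of 0.7 kg, power for a 1.25 kg difference is about 70% with 5, 80% with 6 and 87% with 7 evaluable men per arm. Recruiting 14 therefore keeps about 80% power with one loss per arm, not two.

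If one-sided was intended, say so in both the power statement and the analysis paragraph, and report 82% with five per arm. On either reading, say that the figures depend on the 0.7 kg SD.

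The cost is one paragraph of wording. No patients are added, and the test and endpoint do not change. If the test is two-sided, the stated power becomes less favourable.

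### Section 4.2 implies that 80% power survives the loss of four of 14 men; for the planned t-test, taken as two-sided, it does not, whether dropouts are left out or kept under intent-to-treat with at most half the effect

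*Combined protocol and SAP*

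**What the plan says.** Section 4.2 names the endpoint ("The main endpoint of interest in this study is weight loss") and the analysis principle ("The analyses will follow the intent-to-treat principle"). The sizing follows: "Ten participants (five individuals per treatment arm) would be sufficient to detect a difference of just 1.25kg", at 80% power and "assuming a standard deviation for each groups' weight loss that is slightly higher (± 0.7 kg) than seen in our prior study". The margin comes next: "To account for the potential small dropout rate, we will recruit a total of 14 patients (7 per treatment arm".

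The closing paragraph of Section 4.2 plans two-sample t-tests between arms at P < 0.05, without stating sidedness.

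Three things are not stated:
- a dropout percentage (the rate is only called small);
- how a dropout's weight enters the comparison;
- what diet effect, if any, a dropout is assumed to keep.

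Section 3.1.2 has weights taken at the weekly food pick-up visits, so a man who stops attending may or may not have a usable final weight.

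**The concern.** Recruiting 14 so that ten remain is completer logic: it replaces lost men and assumes that those who remain show the full 1.25 kg difference. Intent-to-treat compares men as randomised. A legume-arm man who stops the diet but is still weighed stays in his arm. If he has lost part of the diet effect, he lowers that arm's mean loss and widens its spread. Extra recruits do not undo this, and the sizing paragraph makes no allowance for it.

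A reader of Section 4.2 will take 80% as protected against four losses. A null result could then be over-read as evidence against a 1.25 kg difference, and the full-scale trial that this pilot is meant to inform could reuse the same reasoning.

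**Working it through.** **Inputs from Section 4.2:** difference 1.25 kg; SD 0.7 kg per arm; 5 per arm before the margin, 7 per arm after; alpha 0.05; two-sample t-test. **Assumed:** two-sided test; dropouts who are kept retain a fraction r of the 1.25 kg, from 0 to 0.5; control dropouts unchanged.

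**1. The plan's own figure.** Normal approximation: n per arm = 2(1.960 + 0.842)² × 0.7² / 1.25² = 4.9, rounded up to 5. Power at 5 per arm: 1.25 / (0.7 × √(2/5)) = 2.82, and Φ(2.82 − 1.96) = 80.6%. N and power both reproduce.

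**2. Same inputs, planned test.** Noncentral t with 8 df and noncentrality 2.82: 69.7% two-sided, 82.4% one-sided. Moving from the normal approximation to the two-sided t-test therefore costs 80.6 − 69.7 = 10.9 points before any dropout is considered.

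**3. Size of the margin.** (14 − 10)/14 = 28.6%, or two of seven per arm. This is the largest loss the margin covers, not a rate that the plan predicts.

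**4. Dilution.** With k of 7 legume-arm men keeping a fraction r, the mean difference is 1.25 × (7 − k + kr)/7. For k = 2:
- r = 0: 1.25 × 5/7 = 0.893 kg
- r = 0.25: 1.25 × 5.5/7 = 0.982 kg
- r = 0.5: 1.25 × 6/7 = 1.071 kg

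The legume-arm variance rises as well. For k = 2, r = 0 it is 0.49 + (2/7)(5/7)(1.25²) = 0.809, which gives a pooled SD of √((0.49 + 0.809)/2) = 0.806 kg.

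**5. Power.** The t-test figures use the noncentral t where every analysed man has the full effect, and simulation of the two-sample t-test where dropouts are kept (400,000 runs for two per arm). The normal column uses Φ(d / (0.7√(2/n)) − 1.96), with SD held at 0.7.

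| Case | n per arm | Difference (kg) | t-test, two-sided | Normal, SD 0.7 |
|---|---|---|---|---|
| No dropout | 7 | 1.25 | 86.5% | 91.6% |
| One per arm, left out | 6 | 1.25 | 79.6% | 87.1% |
| One per arm, kept, r = 0 | 7 | 1.071 | about 67% | 81.7% |
| One per arm, kept, r = 0.5 | 7 | 1.161 | about 80% | 87.3% |
| Two per arm, left out | 5 | 1.25 | 69.7% | 80.6% |
| Two per arm, kept, r = 0 | 7 | 0.893 | 45.7% | 66.5% |
| Two per arm, kept, r = 0.25 | 7 | 0.982 | 59.7% | 74.7% |
| Two per arm, kept, r = 0.5 | 7 | 1.071 | 71.8% | 81.7% |

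The normal column leaves out the wider spread. With the pooled SD of 0.806 the r = 0, two-per-arm entry becomes 54.5%.

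**6. Like-for-like effect of dilution, two per arm, against ten completers.**
- r = 0: t-test 69.7% to 45.7% (24.0 points lost); normal 80.6% to 66.5% (14.1 lost).
- r = 0.25: 10.0 and 5.9 points lost.
- r = 0.5: no loss (69.7% to 71.8%; 80.6% to 81.7%).

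Break-even on the normal scale solves (5 + 2r)/7 = √(5/7), so r = 0.46. Linear interpolation of the t-test results gives 0.25 + 0.25 × (69.7 − 59.7)/(71.8 − 59.7) = 0.46. Dilution costs power only if dropouts keep less than about 45% of the effect.

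**The case against.** A reader might infer that intent-to-treat takes power from 80% down to 46–72%. The documents do not support that. The 80% is a normal-approximation figure and the range comes from a t-test, so about 11 points of the gap are a change of method. At the upper end, like for like, nothing is lost.

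Further points on the plan's side, which stand:

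- The plan's arithmetic is not wrong. Five per arm and 80% reproduce.
- Section 4.2 does not say that 1.25 kg is the difference in adherent men. If it is the difference among all randomised men, dropouts included, then 14 analysed men have 86.5% (t) or 91.6% (normal), above the stated 80%.
- Naming intent-to-treat does not show that all 14 enter the t-test. There is no rule for missing final weights. If dropouts have none and are left out, the ten-completer figure applies and the margin is coherent on its own terms.
- The plan calls dropout small. Four losses is the limit of the margin. With one loss per arm, t-test power is about 80% if left out and 67–80% if kept.
- Sidedness is not stated. One-sided, ten completers have 82.4%, and two kept dropouts per arm give about 62–83%.
- Control dropouts are modelled as unchanged. Both arms follow weight-loss plans (Section 2.2.1), so control dropouts could also lose less weight. That would lessen the dilution but widen the control arm's spread.

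These points narrow the claim but do not remove it. On the two-sided t-test, with 1.25 kg read as the completers' difference and two lost per arm, power is below 80% both when dropouts are left out and when they are kept with up to half the effect.

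**Conclusion.** The point holds in limited form. The sizing sentence and the intent-to-treat sentence do not describe the same analysis, and the implied assurance of 80% power after four losses fails for the planned test if it is two-sided. Part of the shortfall comes from the normal approximation. Dilution adds to it only when dropouts keep less than about 45% of the effect, and its like-for-like cost at the worst end is 14 points (normal, SD held) to 24 points (t-test).

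This rests on the plan's SD of 0.7 kg, on reading 1.25 kg as the completers' difference, on an assumed retained effect of none to half, and on two losses per arm as the outer case. It does not show that the pilot's sample size must change, nor that four men are expected to be lost.

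**What to change.** Keep N at 14. In Section 4.2:

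1. Say whether the 1.25 kg applies to completers or to all randomised men.
2. Say how a dropout's weight enters the intent-to-treat comparison, since the power figure depends on it.
3. Replace the statement of 80% with ten men plus four for dropout by t-test power for that comparison, naming the method, sidedness, assumed dropout and assumed retained effect.

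If 1.25 kg is the completers' difference, possible wording is: *Fourteen men are randomised and analysed by intent-to-treat. For a 1.25 kg difference in completers, SD 0.7 kg and a two-sided two-sample t-test at 0.05, power is about 86% with no dropout. If dropouts remain in the analysis and keep none to half of the effect, it is about 67–80% with one dropout per arm and 46–72% with two. If they have no final weight and are left out, it is about 80% and 70%.*

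The cost is a few sentences, with no extra men or procedures. The downside is a less favourable stated power if dropout is more than minimal.
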